Spinal cord injuries lead to a host of primary and secondary physical impairments that can interfere with an individual's health and participation in life activities. Even with intensive rehabilitation many persons affected by spinal cord injury (SCI) will lead sedentary lifestyles. Individuals with SCI face a multitude of challenges due to physical difficulties that impact their health, independence, and satisfaction with life. With the integration of modern technology into rehabilitation, multiple techniques have been developed that combine our knowledge of walking with robotic technology. Further, emerging research indicates that application of electrical stimulation directly to the spinal cord can result in active motor recruitment below the level of injury for individuals with complete SCI.¹⁻² Non-invasive electrical stimulation, transcutaneous spinal direct current stimulation (tsDCS), has the ability to alter spinal reflexes and modulate spinal cord excitability in healthy subjects and individuals with SCI.³⁻¹⁷ Therefore, tsDCS has the potential to modulate and induce spinal cord excitability and neuroplasticity that leads to recovery after SCI. The purpose of this study is to determine whether tsDCS is safe for individuals with SCI. In specific Aim 1, we will determine whether tsDCS is safe for patients with SCI. In specific aim 2, we will investigate the potential neurophysiological changes and functional improvements in gait for individuals with SCI after combined application of tsDCS and exoskeleton assisted gait training. We hypothesize that when subjects are receiving the tsDCS in combination with exoskeleton training they will demonstrate an increased magnitude in spinal reflex which will correlate with improvement in gait speed, as compared to when subjects are receiving exoskeleton training without tsDCS.

BACKGROUND INFORMATION

As of 2014, there were an estimated 276,000 persons in the United States living with a SCI, and an additional 12,500 new cases added each year. Of those injured, approximately 66%

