In spite of the fact that the spinal cord has shown great potential for neuroplasticity, no one intervention has proven successful at inducing changes in the cord and return of full pre-injury function prior to SCI. It is important to make available in the clinic interventions that combine neuroplasticity principles and focus on restoring function after neurological injury. Electrical stimulation is currently readily available and utilized in the clinic for spasticity, pain, muscle strengthening and neurological recovery. Electrical stimulation can be applied at the muscle, nerve or spinal level. Exciting new research is demonstrating that application of electrical stimulation directly to the spinal cord can result in active motor recruitment below the level of injury for individuals with complete SCI.¹⁻² However, this technology is only available in research phase and requires invasive surgery.

An alternative non-invasive method for stimulating the spinal cord is through the use of transcutaneous spinal direct current stimulation (tsDCS). tsDCS applies electrical current to the spinal cord via surface electrodes placed on the skin. It has been demonstrated in animal models and healthy human subjects that tsDCS has the ability to alter spinal reflexes and has an effect on spinal cord excitability.³⁻¹⁶ The use of tsDCS has been evaluated in healthy individuals, however there is only one research study to date that investigates the use of tsDCS on individuals with SCI.¹⁷ Hubli found that individuals with complete SCI demonstrated changes in spinal reflexes after application of tsDCS.¹⁷ This means tsDCS has the potential to alter spinal cord excitability below the level of lesion.

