Although this technology has been around for decades and tsDCS has been shown to modulate the excitability of the spinal cord, limited research has investigated its use in the SCI population. Before this technology could promote recovery after SCI, further research is needed to evaluate the safety and efficacy of this intervention. Therefore, the purpose of this pilot study is to determine whether tsDCS is safe for individuals with SCI. It is hypothesized that use of tsDCS will lead to measurable changes in spinal excitability (measured by H-reflex in soleus muscles) in individuals with SCI. We further hypothesize that this potential neurophysiological change could lead to gait improvements. To answer our questions, we will use exoskeleton assisted gait training as a standard gait training intervention in combination with tsDCS.

OBJECTIVES

The purpose of this study is to determine whether tsDCS is safe for individuals with SCI.

Specific Aim 1: To determine whether tsDCS is safe for patients with SCI. There is one study that has utilized tsDCS in 17 individuals SCI¹⁷. No adverse events were noted in this study, therefore we hypothesize that all subjects will tolerate the use of tsDCS without adverse reactions.

Specific Aim 2: To investigate the potential neurophysiological changes and functional improvements in gait for individuals with SCI after combined application of tsDCS and exoskeleton assisted gait training. It has been demonstrated that use of tsDCS has an impact on spinal excitability, however there has been no investigation on the potential impact changes in spinal excitability may have on functional mobility. We hypothesize that when subjects are receiving the tsDCS in combination with exoskeleton training they will demonstrate an increased magnitude in spinal reflex which will correlate with improvement in gait speed, as compared to when subjects are receiving exoskeleton training without tsDCS.

STUDY DESIGN

A single case series design (baseline, intervention, and combined intervention) is used in this pilot study. The study schematic diagram is presented in Figure 1.

STUDY POPULATION

We plan to enroll 4 human subjects (male and/or female), age 18 years or older, with a confirmed diagnosis of chronic motor incomplete SCI, classified by the American Spinal Injury Association Impairment Scale (AIS) grades C or D.

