(10MWT). Subjects will participate in two types of training visits; exoskeleton training and exoskeleton training plus tsDCS. Training visits will be scheduled for 0.5-1.5 hours depending on the intervention condition (exoskeleton training or exoskeleton training and tsDCS intervention). There will be a 1 week wash out period between intervention conditions. See Table 1 and 2 for timeline.

Table 1: Timeline for subjects 1 and 3: A-BC-C-BC design

Sub 1 (cathode) and Sub 3 (anode)		A-BC-C-BC							A = Baseline, B = tsDCS, C = Ekso		5 weeks, 17 visits, 17.5 hours								
Visit	1/A	2/A	3/BC	4/BC	5/BC	6/BC	7/BC	Wash out	8/C	9/C	10/C	11/C	12/C	Wash out	13/BC	14/BC	15/BC	16/BC	17/BC
Day	1	5	8	9	10	11	12		22	23	24	25	26		36	37	38	39	40
Time	1 hr	1 hr	1.5 hr	1 hr	1 hr	1 hr	1.5 hr		1 hr	.5 hr	.5 hr	.5 hr	1 hr		1.5 hr	1 hr	1 hr	1 hr	1.5 hr
H-Reflex	X	X	X				X		X				X		X				X
10MWT	X	X	X				X		X				X		X				X
Ekso									X	X	X	X	X						
Ekso + tsDCS			X	X	X	X	X									X	X	X	X

Table 2: Timeline for Subjects 2 and 4: A-C-BC-C design

Sub 2 (cathode) and Sub 4 (anode)		A-C-BC-C						A = Baseline, B = tsDCS, C = Ekso		5 weeks, 17 visits, 15 hours										
Visit	1/A	2/A	3/C	4/C	5/C	6/C	7/C	Wash out	8/BC	9/BC	10/BC	11/BC	12/BC	Wash out	13/C	14/C	15/C	16/C	17/C	
Day	1	5	8	9	10	11	12		22	23	24	25	26		36	37	38	39	40	
Time	1 hr	1 hr	1 hr	.5 hr	.5 hr	.5 hr	1 hr		1.5 hr	1 hr	1 hr	1 hr	1.5 hr		1 hr	.5 hr	.5 hr	.5 hr	1 hr	
H-Reflex	X	X	X				X		X				X		X				X	
10MWT	X	X	X				X		X				X		X				X	
Ekso			X	X	X	X	X									X	X	X	X	X
Ekso + tsDCS									X	X	X	X	X							

Screening

After informed consent is provided, the subject will undergo a screening evaluation to assess skin integrity, hip, knee, and ankle range of motion, and spasticity. We will also perform assessments of functional mobility and measurements to ensure the individual will safely fit inside the robotic exoskeletons.

Baseline Visits

Subjects will participate in two baseline visits, 4 days apart. The visit will last 1 hour and will include assessment of soleus H-Reflex and 10 meter walk test on arrival and 40 minutes after initial assessment. Subjects will be asked to minimize their activity between assessments by either sitting in a chair or lying on a mat.

Training Visits

Each training visit will involve either an exoskeleton intervention or a combined exoskeleton and tsDCS intervention. Subjects will participate in a total of 15 training visits.

[figure not shown]

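### Does Aim 2's prediction of a larger spinal reflex, made without regard to polarity when two subjects receive cathode and two anode, leave the verdict open to choice?

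*Combined protocol and SAP*

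**What the plan says.** The H-reflex prediction appears in two strengths.

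- **Directional.** Specific Aim 2 in Objectives says that "when subjects are receiving the tsDCS in combination with exoskeleton training they will demonstrate an increased magnitude in spinal reflex". The opening summary words it the same way and adds the link to gait: "they will demonstrate an increased magnitude in spinal reflex which will correlate with improvement in gait speed". The comparison is with exoskeleton training alone.
- **Non-directional.** The last paragraph of the Background hypothesises that "use of tsDCS will lead to measurable changes in spinal excitability", measured by the soleus H-reflex.

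The supporting rationale is also non-directional. In the Background, "tsDCS has the ability to alter spinal reflexes and has an effect on spinal cord excitability", and in the one cited study in spinal cord injury, "individuals with complete SCI demonstrated changes in spinal reflexes after application of tsDCS". Under Specific Aim 2: "It has been demonstrated that use of tsDCS has an impact on spinal excitability".

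Polarity is set in the table headers under Procedures. Table 1 (sequence A-BC-C-BC) has "Sub 1 (cathode) and Sub 3 (anode", and Table 2 (sequence A-C-BC-C) has "Sub 2 (cathode) and Sub 4 (anode". The tsDCS Intervention paragraph says that subjects are assigned to one or the other, and gives no expected effect for either.

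Statistics is one sentence. It plans a descriptive look at the trend of the outcomes across baseline, intervention and combined intervention, separately for each case series. It does not mention polarity.

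**The concern.** Polarity is varied deliberately and balanced across the two sequences, yet no hypothesis and no line of the analysis refers to it. Nothing in the readable text explains why both polarities should raise the reflex. The title of item 11 in Literature Cited says that an H-reflex effect depends on current polarity. It concerns a different measure (post-activation depression), so it shows only that the question could have been foreseen.

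Three things would be at stake.

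- If one polarity raised the reflex and the other lowered it, the investigators could report that Aim 2 was met in half the subjects or that the Background hypothesis was met in all. They could choose between these after seeing the data.
- For a polarity that lowers the reflex, Aim 2 does not say what gait-speed change to expect.
- A summary taken over a sequence, or over tsDCS as a whole, would mix the polarities one to one.

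**Working it through.** The documents give no effect size, variance, power or alpha, so there is no figure of the plan's own to reproduce. The check is a count.

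**Inputs (Tables 1 and 2).** Subject 1: cathode, A-BC-C-BC. Subject 2: cathode, A-C-BC-C. Subject 3: anode, A-BC-C-BC. Subject 4: anode, A-C-BC-C. That is two subjects per polarity and one in each polarity-by-sequence cell.

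**Step 1: when do the two statements disagree?** Assume that each polarity acts the same way in both of its subjects: reflex up, unchanged or down. There are 3 × 3 = 9 patterns. An increase meets Aim 2's direction; any change meets the Background statement.

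| Anode / cathode | Subjects with increase | Subjects with change | Verdicts for all four subjects |
|---|---|---|---|
| up / up | 4 of 4 | 4 of 4 | both met |
| up / down | 2 of 4 | 4 of 4 | **differ** |
| down / up | 2 of 4 | 4 of 4 | **differ** |
| down / down | 0 of 4 | 4 of 4 | **differ** |
| up / none | 2 of 4 | 2 of 4 | neither met |
| none / up | 2 of 4 | 2 of 4 | neither met |
| down / none | 0 of 4 | 2 of 4 | neither met |
| none / down | 0 of 4 | 2 of 4 | neither met |
| none / none | 0 of 4 | 0 of 4 | neither met |

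Aim 2's direction holds in all subjects in 1 of 9 patterns and the Background statement in 4 of 9, so they disagree in 4 − 1 = 3. One of these (down / down) does not depend on polarity, which leaves 2 of 9. If both polarities raise the reflex by different amounts, both statements are met. A polarity-dependent response therefore does not by itself split the verdict; opposite directions do. These are counts of patterns, not probabilities.

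**Step 2: does the planned analysis mix polarities?** With effect d for one polarity and −d for the other, a mean weighted one to one is (d − d)/2 = 0, so pooling could hide an effect. But no mean over subjects, over a sequence or over tsDCS is planned. Study Design and Procedures describe a case series with phases, and Statistics describes trends within it. Each subject keeps one polarity in every tsDCS phase, so the contrast of tsDCS phases with exoskeleton-only phases is made within one polarity.

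**Step 3: would a direction per polarity strengthen the evidence?** As an illustration, suppose there is no effect, up and down are equally likely, and subjects are independent. All four match one common predicted direction with probability 0.5^4 = 0.0625. All four match polarity-specific directions with the same probability, 0.0625. Within one polarity, both subjects match with probability 0.5^2 = 0.25. Polarity-specific predictions add no strength for the four subjects together. With two subjects per polarity, a polarity difference cannot be separated from differences between people.

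**The case for a change.** The strongest case for a change is that it costs a few sentences and closes a real ambiguity. Showing results per subject displays the data but does not say which statement each subject is judged against. The phrase in Statistics about each case series is not defined. Study Design treats the whole study as one series, and a reader could take each table's sequence as the unit, which puts one cathode and one anode subject together. Aim 2 speaks of subjects receiving tsDCS without limiting the claim to one polarity, so applying it to all four is a natural reading.

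Some of this stands. The text is silent on how to read opposite directions, and Aim 2 leaves the gait-speed expectation undefined where the reflex falls.

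The rest is weaker. An increase is one kind of change, so the two statements do not conflict; the Background sentence is a general lead-in to the specific aim. Aim 1 says all subjects in its hypothesis and Aim 2 does not, so an all-subjects criterion is a possible reading, not a stated rule. Even if a sequence were the unit, it would consist of two individual records whose polarities are printed in the table header.

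**Conclusion.** No change is needed. The wording gap is real but small. It matters only if the H-reflex falls under at least one polarity, and as a polarity question only if the two polarities act in opposite directions (2 of the 9 patterns). In that case the natural report is that the predicted increase was seen in two of four subjects, with each subject's polarity shown. Anyone following the plan can write that from the four records and the table headers.

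Adding a direction for each polarity, or labelling the result exploratory, would alter no measurement, no within-subject contrast and no summary that the plan calls for. The stated purpose is safety, Aim 2 is framed as an investigation of potential changes, and nothing is tested or decided on the H-reflex.

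This rests on two assumptions: that the case series is read subject by subject, and that the report does not average over subjects of different polarity. If a pooled tsDCS mean were later presented as the Aim 2 result, the polarity question would become material. How people are placed in subject slots 1 to 4 cannot be judged, because Figure 1 is not shown in the available copy.

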
 • Male or non-pregnant female • ≥18 years of age • Able to achieve adequate fit within exoskeleton • Diagnosis of spinal cord injury, T10 level and above (T11 and 12 may participate if no clinical signs of lower motor neuron lesion present) • Minimum of 6 months post injury • Sufficient range of motion to attain normal, reciprocal gait pattern, and transition from normal sit to stand or stand to sit • Weight <220 pounds • Intact skin on all surfaces in contact with device and load bearing surfaces • Ability to perform informed consent 	
 • Pregnancy • Spinal instability • Unhealed limb or pelvic fractures or any condition restricting weight bearing in limbs • Presence of peripheral neuropathy or any pathology that could influence reflex excitability • Diagnosis of other neurological injury other than SCI such as CVA, MS, ABI, CP • Uncontrolled spasticity (≥3 on Modified Ashworth Scale) • Colostomy • Decreased range of motion or contractures in legs (>10° at hips, knees or ankles) • Uncontrolled autonomic dysreflexia • Unresolved deep vein thrombosis • Inability to tolerate standing due to cardiovascular issues or orthostatic hypotension • Severe comorbidities: active infections, heart, lung, or circulatory conditions • Pressure sores, impaired skin integrity • Use of mechanical ventilation for respiratory support • Presence of any of the following contraindications to electrical stimulation: cardiac pacemaker, deep brain stimulator, or evidence of cancerous (malignant) tissue • Presence of metal in thoracic spine or region of electrode placement

Procedures

The proposed investigation is a single case series design (baseline, intervention, combined intervention). The study schematic diagram is presented in Figure 1.

Subjects will be asked to attend a screening visit, 2 baseline visits and 15 training sessions. The screening visit will take 30 – 45 minutes and assessment of range of motion, flexibility, spasticity, mobility, and measurements will be performed to ensure individual will fit inside the robotic exoskeleton. Baseline visits will be scheduled for 1 hour and will include spinal reflex testing using the Soleus Hoffman Reflex (H-Reflex) and a 10 Meter Walk Test

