Exoskeleton Intervention: Each exoskeleton intervention will last 20 minutes. During the exoskeleton training session, subjects will wear Ekso[®], a lower extremity exoskeleton robotic walking device. Initial training will focus on static and dynamic standing balance and weight shift training with the exoskeleton and progress to more difficult activities such as transitioning from sit-to-stand and stand-to-sit, walking, and turning. There will always be at least one trainer present during the training sessions to provide varying levels of assistance. As a subject's skill with the powered exoskeleton improves, the need for trainer assistance will be proportionately reduced. At the conclusion of 20 minutes of exoskeleton gait training, the subject will perform a 10 Meter Walk Test.

Safety: There will always be at least one trainer present during the training sessions to provide varying levels of assistance. A 2nd staff will stand and walk with the subject if needed to ensure safety and prevent falls. Subjects will wear a safety harness attached to an overhead body weight support system to prevent falls if necessary.

tsDCS Intervention: tsDCS interventions will last 20 minutes. Subjects will be assigned to receive anode or cathode stimulation. Direct current stimulation will be delivered using Soterix Medical 2x1s Transcutaneous Spinal Direct Current Stimulator. Stimulation will be provided following published tsDCS protocol^{7,17}. One electrode (50 cm²) will be placed along center of spine centered over the spinous processes of T10. The reference electrode will be placed over the R shoulder. Direct current intensity will be applied at 2.5 mA (0.05 mA/cm²) with a total charge of 60 mC/cm² for 20 minutes. These stimulation parameters are below the known threshold for possible tissue damage³⁸.

Subjects will participate in individualized training sessions at UT Health Motor Recovery Laboratory at the NeuroRecovery Research Center at TIRR Memorial Hermann.

Figure 1: Study Schematic Diagram

Outcome Measures

Subjects will participate in a screening, 2 baseline visits and 15 intervention visits. Outcome measures that will occur at baseline and during intervention visits and will include spinal reflex testing using the Hoffman Reflex (H-Reflex) and 10 Meter Walk Test (10MWT).

Assessments:

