- **Soleus H-reflexes:** H-reflex will be elicited by placing the cathode of an electrical stimulator in the popliteal fossa and stimulating N. tibialis. Surface electromyography electrodes will be placed at the soleus muscle of the testing leg to record the electrical-induced muscle activity. At the beginning of the test, stimulus thresholds and maximal amplitudes of H-responses (Hmax) and M-responses (Mmax) will be assessed. The stimulus intensity applied to elicit H-reflexes will be chosen just below stimulus intensity required to elicit Hmax, i.e. 0.9 times. The size of each H-reflex will be measured as the peak-to-peak amplitude of the non-rectified EMG trace (Figure 2). H-reflex magnitude will be normalized by expressing it as a percentage of the amplitude of Mmax.

[figure not shown]

Figure 2. An illustration of H-reflex and preceding M-wave elicited from a patient with SCI

- **10 Meter Walk Test (10MWT):** The 10MWT will assess subject's gait speed. Four marks will be placed on the ground at 0, 2, 12 and 14 meters. Subjects will walk a total of 14 meters. The middle 10 meters (between marks at 2 and 12 meters) will be timed and recorded as their gait speed. Subjects will perform a 10MWT without use of exoskeleton.
- **Exoskeleton user feedback:** A questionnaire will be administered to allow participants to provide feedback regarding their experience after completion of treatment sessions.

Treatment sessions: We will track any signs of adverse reaction to the tsDCS intervention such as skin irritation, complaints of pain or discomfort continuously throughout subject's participation.

Tentative Timeline The proposed timeline to complete the study is 2 years.

PHOTOGRAPHY and VIDEOTAPING

We would like to obtain photographs and video during the tsDCS and exoskeleton treatment sessions. The goal of the photography and videotaping will be used for educational

purposes when presenting results of this study. The photographs will be used to demonstrate application of tsDCS and what exoskeleton training looks like. The identity of subjects will not be revealed in the photograph. If a photograph or video is used, a black box will be placed in front of subject's face to protect their identity. Any photographs and videos taken during the study will be saved on a locked computer in a file labeled with the subject's research number and no other identifying information. These files will be saved for five years after which they will be deleted.

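### Pain and discomfort from tsDCS are captured only as complaints, but feeling under the T10 electrode may be reduced in some subjects and is never recorded, so an absence of local complaints is weak support for Aim 1

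*Combined protocol and SAP*

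**What the plan says.** All references are to the combined protocol and SAP.

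- **Aim 1 (Objectives).** The safety hypothesis is taken from one cited study of tsDCS in 17 people with SCI: "No adverse events were noted in this study, therefore we hypothesize that all subjects will tolerate the use of tsDCS without adverse reactions". Tolerance is not defined further.
- **Electrode sites (tsDCS Intervention).** "One electrode (50 cm²) will be placed along center of spine centered over the spinous processes of T10". For the other electrode: "The reference electrode will be placed over the R shoulder".
- **Injury level (inclusion and exclusion chart).** "Diagnosis of spinal cord injury, T10 level and above", with T11 and T12 allowed when there are no clinical signs of a lower motor neuron lesion. Study Population adds motor-incomplete injury, AIS C or D. There is no sensory criterion.
- **Screening (Procedures).** The listed assessments are skin integrity, range of motion, spasticity, functional mobility and exoskeleton fit. None tests sensation at either electrode site.
- **Adverse reactions (Assessments, Treatment sessions).** "We will track any signs of adverse reaction to the tsDCS intervention such as skin irritation, complaints of pain or discomfort", continuously throughout participation.
- **Skin inspection (Data and Safety Monitoring, item 4).** A licensed physical therapist inspects the skin before tsDCS and compares it afterwards. Differences are recorded and followed up with the study physician.
- **Statistics.** Descriptive trends of the outcome measures for each case series. No safety summary is described.

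**The concern.** Aim 1 is the study's stated purpose, and its hypothesis is an absence of adverse reactions. Absence is informative only if the event would have been noticed had it occurred. For skin changes it would be, because a therapist looks. For pain and discomfort it depends on the subject feeling them.

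In a subject injured at T10 or above, the skin under the active electrode can lie at or below the injury level. AIS C or D describes motor function and does not by itself establish normal feeling at that site. If feeling there is reduced or absent, a session without a local complaint says little about local tolerance. Since nothing planned records sensation at the site, the final report could not separate subjects who felt the current and were comfortable from subjects who felt little or nothing. With 4 subjects, one or two in the second group would noticeably change what an absence of complaints means.

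**Working it through.** **1. The plan's own stimulation figures reproduce.** Current density is 2.5 mA / 50 cm² = 0.05 mA/cm². Charge density is 0.05 mA/cm² × 1,200 s = 60 mC/cm². Both agree with the tsDCS Intervention section. No sample-size or power figure is given for Aim 1.

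**2. What each safety component can detect.**

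| Component | How it is captured | Depends on feeling at the site? |
|---|---|---|
| Skin change | Therapist inspection before and after tsDCS | No |
| Pain or discomfort at the T10 electrode | Complaint | Yes |
| Pain or discomfort at the shoulder electrode | Complaint | Yes, but this site may lie above the lesion |
| General symptoms | Complaint | Not on feeling at T10 |

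Only the second row is clearly exposed. The skin inspection does not fill that gap: it compares two time points and cannot show pain that leaves no mark during the 20 minutes.

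**3. Sessions (visit labels, Tables 1 and 2).** Subjects 1 and 3 have combined visits 3–7 and 13–17, which is 10 each. Subjects 2 and 4 have visits 8–12, which is 5 each. The total is 10 + 5 + 10 + 5 = 30.

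| Subjects without feeling at T10 | Sessions in which silence about T10 is uninformative | Sessions remaining for the T10 symptom statement |
|---|---|---|
| 0 | 0 | 30 |
| 1 | 5 or 10 | 25 or 20 |
| 2 | 10, 15 or 20 | 20, 15 or 10 |
| 3 | 20 or 25 | 10 or 5 |
| 4 | 30 | 0 |

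The documents do not say which row applies.

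**4. Illustration of the effect on an absence of complaints.** Let p be the chance that a subject has a painful reaction at the T10 site, k the number of subjects with impaired feeling there, and s the chance that such a subject reports it. Subjects with normal feeling are taken always to report. Then

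P(no T10 complaint in any of 4) = (1 − p)^(4−k) × (1 − p·s)^k.

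All three inputs are assumptions. For example, with p = 0.25, k = 2 and s = 0: 0.75² × 1² = 0.563.

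| p | s | k = 0 | k = 1 | k = 2 | k = 3 | k = 4 |
|---|---|---|---|---|---|---|
| 0.10 | 0 | 0.656 | 0.729 | 0.810 | 0.900 | 1.000 |
| 0.25 | 0 | 0.316 | 0.422 | 0.563 | 0.750 | 1.000 |
| 0.25 | 0.5 | 0.316 | 0.369 | 0.431 | 0.502 | 0.586 |
| 0.50 | 0 | 0.063 | 0.125 | 0.250 | 0.500 | 1.000 |

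Across each row the true reaction rate is constant. Only the ability to report changes.

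**5. What zero local complaints would rule out.** If local complaints are read only in the n subjects with feeling at T10, the one-sided 95% exact upper bound for 0 of n is 1 − 0.05^(1/n): 52.7% for n = 4, 63.2% for n = 3, 77.6% for n = 2 and 95.0% for n = 1. Even the best case is wide, so the effective n should be visible.

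**The case against.** The strongest reply is that the plan does not rest on complaints. Its list of reactions is open-ended and names an observable sign first, and the before-and-after skin inspection works whatever the subject can feel. In a descriptive pilot of 4 subjects, the sensory question is then a detail of interpretation. Much of this stands: the skin part of Aim 1 is unaffected, and the weakness is confined to self-report at one site. It does not remove the gap for pain and discomfort, which have no other means of capture.

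A reader might also go further than the documents allow, in five ways.

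- **That the plan counts silence as tolerance.** No such rule is written. Tolerance is undefined, and the Aim 1 hypothesis merely leaves that reading open.
- **That subjects cannot feel the current.** AIS C or D does not establish this, and no sensory status is given. Reduced feeling is possible, and the range of 0 to 4 includes no effect at all.
- **That every subject is injured at or above the electrode.** T11 and T12 injuries can qualify, and for them the T10 site is above the injury level.
- **That the sessions of an affected subject carry no symptom information.** Complaint capture is not limited to T10. Shoulder and general complaints still count, and the skin data remain valid.
- **That the cited study's clean record reflects missing sensation.** The Background says that "individuals with complete SCI demonstrated changes in spinal reflexes after application of tsDCS", but the documents give neither that study's sensory findings nor how it collected adverse events.

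**Conclusion.** The concern holds in a limited form. Feeling under the T10 electrode may be reduced in some of the 4 subjects, pain and discomfort there are captured only as complaints, and sensation at the electrode sites is not recorded. Absence of local complaints at a site with reduced or absent feeling is therefore weak evidence of tolerance, and the plan provides no way to recognise such a site when the results are read.

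The size cannot be fixed from the documents. It runs from no effect to all 30 sessions for the T10 symptom statement, with 5 or 10 sessions per affected subject. The probabilities in the working depend on assumed reaction and reporting rates and show direction and scale only. The skin-irritation part of Aim 1 stands on all sessions. The point does not undermine the design, but it changes what Aim 1 may conclude about pain and discomfort, so it merits a change to data capture and reporting.

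**What to change.** 1. **Record sensation at screening.** Note light touch and pinprick at the skin under each electrode (T10 spine and right shoulder). Use existing sensory scores if they cover those sites. Otherwise add a brief bedside check alongside the existing skin inspection.
2. **Specify a per-subject safety listing in Statistics.** Report complaints by site (T10, shoulder, general) and by sensory status at that site (normal, reduced, absent). Report skin-inspection findings separately for all planned tsDCS sessions, 30 by visit labels.
3. **Word the Aim 1 conclusion in two parts.** The skin statement uses all sessions. The pain and discomfort statement gives how many subjects and sessions had feeling at the T10 site. Sessions without feeling there should not be dropped from the safety report, because their skin findings remain valid.

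The cost is a brief check per subject, a few fields on the screening form and one split in the listing. Eligibility and stimulation are unchanged. The downside is a smaller denominator for the symptom statement and very small cells, which suits a subject-by-subject listing better than rates.
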